Analysis of the Primary Endpoint 10.4	
Depression – text deleted ...Pediatric depression T- scores will be converted to adult depression T-scores using a published crosswalk linking the scores from the two surveys.
 
Added text: Pediatric depression T- scores will be transformed to the adult scale using a published crosswalk for a combined analysis.
	9/15/2020
Specimen Collection Section 7.4	Clarification that DNA specimen collection should be done after consenting and completed prior to randomization	12/22/2020
Throughout the Document	Removal of Quick Inventory of Depressive Symptomatology (QIDS) depression scale and replaced with Patient Health Questionnaire-8 (PHQ-8) depression scale.	7/2/2021
Protocol Synopsis-Inclusion Criteria Section 1	Acute Pain:	7/2/2021
Inclusion Criteria Section 5.1	
 • Removal of “Elective/planned surgery patients with an upcoming pre-surgery visit” • Removal of “as this is the minimum age at which proposed outcome measures (PROMIS) are validated without parent proxy” at age inclusion • Added clarifying text for targeted opioids for Elective/planned surgery types 	
	
Chronic Pain:
 
 • Added clarifying text for primary 	

	
clinics definition and for treatment of chronic pain with specific opioids
 
 Removed medical diagnosis codes for pain diagnosis, and symptoms 
Depression:
 
 Removal of “as this is the minimum age at which proposed outcome measures (PROMIS) are validated without parent proxy” at age inclusion Added clarifying text for psychiatry and primary clinics definition and depression diagnosis Removed medical diagnosis codes for depression 	
Protocol Synopsis-Exclusion Criteria Section 1 Exclusion Criteria Section 5.2	
Trial Wide:
 
 Include “incarcerated” as an exclusion example for “Are institutionalized or too ill to participate (i.e. mental or nursing home facility) Removal of “Plan to move out of the area within 6 months of enrollment” 
Acute Pain:
 
 Removal of “Plan to move out of the area within 6 months of enrollment” Removal of “Adults with a similar, previous surgery in whom pain control is well defined and a genotype guided approach would not likely be followed” 
Chronic Pain:
 
 Addition of “Plan to move out of the area within 6 months of enrollment” Addition of “Currently taking daily opioids other than tramadol, codeine or hydrocodone” 
Depression:
 
 Addition of “Plan to move out of the area within 6 months of enrollment” Removal of medical diagnosis codes for psychotic, neurocognitive, cognitive developmental delay or disability, seizure and bipolar disorders Removal of antipsychotic medications Removal of “Depression secondary to substance abuse disorder or general medical condition” 	7/2/2021

Protocol Synopsis-Secondary Endpoints Section 1	Depression: • Updated the secondary endpoints using PHQ-8 depression scale	
Secondary Endpoints Section 3.2		
Provider Recruitment and Assent Section 6.1	
Acute Pain:
 
 Refined the text: “Providers with a predominant use of codeine, tramadol and hydrocodone for pain control before and during the 10-day primary endpoint may be approached by qualified study personnel. Providers will be notified per site institutional guidelines that their patients may be contacted by study site recruiters to participate. Surgical procedures where there is persistent pain at the 10-day primary endpoint should be prioritized for inclusion in the study.” 
Chronic Pain:
 
 Removed text “approached by qualified study personnel, and notified that their patients will be contacted by study site recruiters to participate.” Added text: “may be approached by qualified personnel. Providers will be notified per site institutional guidelines that their patients may be contacted by study site recruiters to participate.” 
Depression:
 
 Removed text “They then will be notified that their patients will be contacted by study site recruiters to participate.” Added text “and may be approached by qualified study personnel, and given the opportunity to participate as a study provider. Providers will be notified per site institutional guidelines that their patients may be contacted by study site recruiters to participate.” 	7/2/2021

Baseline Participant Assessments Section 7.2
	
Baseline:
 
 Removed text “baseline data will be collected” Added text “survey data will be collected” 
Past Medical History:
 
 Removed text “in the medical record.” Added text: See MOP for details.” 
Baseline medication:
 
 Added text “the EHR and/or participant self-report.” 	
7/2/2021


Follow-up Participant Assessment All Trials Section 7.3
	
All Trials: Medications:
 
 Removed text “patient surveys at the primary endpoint time points: at baseline, 10-days and 1-month, 3-months and 6-months for the acute pain participants, and baseline, 1-month, 3-months and 6-months for the chronic pain and depression participants.” Added text “patient surveys at baseline and the primary endpoint time points: 10-days for Acute Pain and 3-months for Depression and Chronic pain.” 
Acute Pain:Opioid Consumption Questionnaire:
 
 Removed text 
 “the date the prescription was filled” “Study participants will also be asked to read the tablet strength from their prescription bottle but this will be verified by local study coordinators by reviewing the EHR for the prescription written.” 
Depression:
 
 Removed reference text to the QIDS: “Quick Inventory of Depressive Symptomatology: A 16 item survey completed by the participant assessing depression symptoms[38]. This survey will be administered at baseline, 3 months, and 6 months post return of results. Added reference text for the PHQ-8: “Patient Health Questionnaire-8 – An 	
7/2/2021

	8 item survey completed by the participant assessing depression symptoms over the last two weeks. This survey will be administered at baseline, 3 months, and 6 months post return of results[38].	
Data Collection from Electronic Health Record Section 7.8	
 Removed text: “Data from the local EHR will be used to assess participant’s medications, medication changes, medication discontinuations, and, if available, reasons for medication discontinuations” Added text: “Data collected from the local EHR will include prescription information and encounters including clinic visits, hospitalizations, and emergency department visits and associated diagnoses” 	7/2/2021
Table 8. Data Collection Schedule	
 Updated the Data Collection Timing for the Acute Pain and Immediate Chronic Pain and Depression arms. Including timings for Delayed Chronic Pain and Depression arms Updated the data collection schedule for the Assessment of Prescriptions 	7/2/2021
Safety Assessment and Monitoring-Events of Interest Section 8.2	
Redefined the text to:
 
 “Participant reported emergency department visits and hospitalizations will be collected in the 1, 3, and 6-month follow-up participant surveys. EHR will be used as an additional source for emergency department visits and hospitalizations, up to approximately 12 after the last patient is randomized. For the details of collecting EHR data, see Protocol section 7.8 and MOP. EHR results will be sent to the CC via secure data transfer and formatted for data analyses.” 	7/2/2021
Statistical Analysis Plan and Sample Size: Analysis of Secondary Endpoints Section 10.5	
Depression:
 
 Added text “and achieving 5% reduction in PHQ-8 scores “and “PHQ-8 scores” 	7/2/2021

Data Management: Data Entry and Record Keeping Section 11.1	
 Removed text: “automatically “ and “To verify the accuracy of automatic import of results into the participant’s records, laboratories will also transfer raw data in whatever format produced locally to the CC via secure file transfer after the first patient sample has been processed and at other intervals as described in the MOP.” Added text: “The accuracy of the import of laboratory results will be verified by comparing the results recorded in the study database to an external record of the result for a subset of the study participants. See MOP for details.” 	7/2/2021
Data Management: Data Element Definitions Section 11.2	
Depression Remission:
 
 Added text: B. Whether or not the PHQ-8 scores are ≤ 4, which is equivalent to depression severity being none-mild.” Added term definition: “Depression (PHQ-8) score: The sum of the responses to the PHQ-8 survey, range from 0 to 24.” Removed text in Opioid Usage: “and post discharge inpatient opioid usage immediate post-surgery collected from EHR queries” 	7/2/2021
References	Removed reference for QIDS depression scale and added in reference for PHQ-8 depression scale.	7/2/2021
Title page; Protocol Version and Amendment Tracking; Investigator Statement; Abbreviations; Protocol Synopsis;	
 Reformatted the entire document and updated page numbers Title page updates and PI names Protocol Version and Amendment Tracking -- Added Amendment 6 change information Investigator_Statement–updated protocol version date Abbreviations corrected typo Protocol Synopsis – Study Population updated the enrollment numbers to reflect the update milestones 	8/30/23

Updates found in Protocol Clarification Memo #2- 28Aug2021 in Protocol Synopsis, Study Population, and Inclusion/Exclusion Criteria Section 5 and Study Procedures
	
 • Updated Inclusion criteria for Depression: 
 ◦ Remove “the last” from “Evidence of depressive symptoms for at least the last 3 months based on patient interview or documentation in electronic health records” • Updated Exclusion criteria: 
 ◦ Add to Trial wide: Any other medical, behavioral, or developmental condition that in the opinion of the investigator may confound study data/assessments ◦ Add to Chronic Pain: Include “for treatment of pain” to “Currently taking daily opioids other than tramadol, codeine, or hydrocodone for treatment of pain” ◦ Add to Chronic Pain: Include “Using a pain pump” • Updated text for baseline participant assessments in Section 7.2 	

Updates found in Protocol Clarification Memo #3- 22Oct2021 in Protocol Synopsis-Inclusion/Exclusion Criteria and section 5.2 Exclusion Criteria
	
 • Updated Exclusion criteria: removal of “Undergoing a laparoscopic surgery” 	8/30/23

Section 7 Study Procedures
	
 • Section 7.1 Interventions/Treatments: Table 2 Corrected a typo in the table • Section 7.2: Baseline medications- Simplified the text by removing “Additionally, participant prescription and over the counter medications may be collected using patient surveys.” And adding “See MOP for details.” • Section 7.3: Follow-up Participant Assessments All Trials Medications: Removed “prescription and over the counter” • Section 7.4: Specimen Collection- corrected verb tense. • Section 7.8: Data Collection from the Electronic Health Record-corrected text from “baseline” to “time-zero”. • Section 7.9 Table 8. Data Collection Schedule-- Reverted the Table 8 to 	8/30/23

	the prior version—removed the specific timing from the last amendment	
Section 8: Safety Assessment and Monitoring	
 Revised the language to reflect what type of Adverse Device Effect (ADE) and unanticipated Adverse Device Effect (UADE) events to be reported to the IRB based on the trial regulated under an Abbreviated Investigational Device Exemption. Section 8.2: Event of Interest: clarified the text to “EHR may be used...” and the timing of the data collection 	8/30/23
Section 9: Medicare and Medicaid Claims Data Collection and Analysis	
 Added in clarifying text for the Medicare and Medicaid data collection and analysis. 	8/30/23
Section 10: Statistical Analysis Plan and Sample Size	
 Section 10.1: Sample Size Determination: Added language to define the mITT population and updated the enrollment numbers to reflect the update milestones Table 9: Sample size calculations: updated the numbers 	8/30/23
Title page; Protocol Version and Amendment Tracking; Investigator Statement;	
 Title page updates Protocol Version and Amendment Tracking -- Added Amendment 7 change information Investigator Statement—updated protocol version date 	10/9/23
Section 6.3: Participant Discontinuation/Withdrawal from the Study	
 Removal of “that is \geq 3 months”. 	10/9/23
Title page; Protocol Version and Amendment Tracking; Investigator Statement;	
 Title page updates Protocol Version and Amendment Tracking -- Added Amendment 8 change information Investigator Statement—updated protocol version date 	
Throughout the Document	
 Corrected 4 instances of ADOPT-PGx to ADOPT PGx 	

Section 10.6: Other Planned Analyses	
 Added a couple of primary research exploratory analyses Updated exploratory endpoints or comparison of endpoints Updated sub-groups 	
Section 12.3: Confidentiality and Privacy	
 Updated language to reflect what is occurring in the study. Removed the text: and all identifiers, data, and keys will be placed in separate, password protected/encrypted files and each file will be stored in a different secure location. 	

1. PROTOCOL SYNOPSIS

Protocol Title	A Depression and Opioid Pragmatic Trial in Pharmacogenetics (ADOPT-PGx)
US IND Number	
Grant Number	
Product/Intervention	Immediate vs. delayed pharmacogenetic testing and genotype-guided pain or depression therapy
Objectives	
Acute Pain:
 
 • To determine the effect of genotype-guided therapy on pain control and use of DEA schedule II opioids in post-surgical participants 
Chronic Pain:
 
 • To determine the effect of genotype-guided therapy on pain control in chronic pain participants 
Depression:
 
 • To determine the effect of genotype-guided selection and dosing of antidepressants on control of depression in participants with ≥ 3 months of depressive symptoms who require new or revised therapy 
All Trials:
 
 • To determine the effect of genotype-guided therapy for opioids, antidepressants, and optional additional, CPIC gene-drug pairs on overall well-being • To determine the effect of genotype-guided therapy for opioids, antidepressants, and optional additional, CPIC gene-drug pairs on healthcare utilization
Study Design	ADOPT PGx is comprised of three separate trials, Acute Pain, Chronic Pain, and Depression. Each trial is a prospective, multicenter, two arm randomized pragmatic trial. For all trials, participants will be randomized in a 1:1 ratio to immediate pharmacogenetic testing and genotype-guided therapy (Intervention arm) or 6-month delayed testing on participants receiving standard care (Control arm). In each trial, the primary outcome comparison will be between the intervention group (i.e. immediate testing) and control group (i.e. delayed testing) in the subset of participants with actionable phenotypes, within each study.
Rationale for Study Design	Pain and depression are conditions that impact substantial proportions of the US population and have challenges associated with identifying the right therapy while minimizing adverse effects or opioid addiction. There is evidence that both opioid and antidepressant prescriptions can be guided by pharmacogenetics (PGx) data based on existing guidelines from the Clinical Pharmacogenetics Implementation Consortium (CPIC). Using such an approach, a recent single site Pragmatic Clinical Trial (PCT) demonstrated that among CYP2D6 poor (PM) and intermediate

	
metabolizers (IM), there was greater improvement in pain control in the genotype-guided arm compared to usual care arm[1]. Similarly, existing studies of PGx tailored antidepressant therapy suggest that the genotype-guided approach is superior to usual care in remission and/or response rates, however these studies are small and often industry-sponsored.
 
A broader trial is needed to determine the importance of PGx testing and genotype guided therapy for improving symptom management (i.e. pain control or control of depression symptoms), DEA schedule II opioid use, well-being, and overall healthcare utilization.

Study Population	
Acute Pain Randomized Population Approximately 1730* participants with planned/elective surgery who are anticipated to start a paincontrol medication with existing CPIC guidelines after their surgery
 
Analytical Population Approximately 304 participants from the randomized population who have an actionable phenotype defined as CYP2D6 IM or PM (i.e. CYP2D6 activity score ≤ 0.75)
 
Chronic Pain Randomized Population Approximately 985* participants see in primary care or pain specialty clinics who are already prescribed or anticipated to be prescribed tramadol, codeine, or hydrocodone for pain control.
 
Analytical Population Approximately 268 participants from the randomized population who have an actionable phenotype defined as CYP2D6 IM or PM (i.e. CYP2D6 activity score ≤ 0.75)
 
Depression Randomized Population Approximately 1540* participants seen in primary care or psychiatry clinics who are already prescribed or anticipate to be prescribed an SSRI with existing CPIC guidelines
 
Analytical Population Approximately 542 participants from the randomized population who have an actionable phenotype, defined as a CYP2D6 PM or ultra-rapid metabolizer (UM), or a CYP2C19 PM, rapid metabolizer (RM), or UM

	*Subject to change based on the actionable phenotype rates and missing data.
Number of Sites	11 sites with approximately 60-80 clinics
Duration of Subject Participation:	Up to one year from consent to end of follow-up

Description of implementation of intervention (e.g.,	The intervention for ADOPT PGx is the immediate return of PGx testing results to the participant's healthcare provider.
dose, schedule, etc.)	
The PGx testing is comprised of Clinical Laboratory Improvement Amendments (CLIA) validated, panel-based genetic testing of two required genes, CYP2D6 and CYP2C19. The resulting CYP2D6 genotypes will be converted to enzymatic activity scores and the activity scores converted to metabolizer phenotypes after also taking strong and moderate CYP2D6 enzyme inhibitor drug interactions into account. The CYP2C19 genotypes will be converted to metabolizer phenotypes.
 
The results of the PGx test will be returned to the healthcare providers using standard site-specific laboratory return of results methods, a static report with both interpretation and recommendations, and where possible, interruptive clinical decision support (CDS) alerts within the electronic healthcare system. Both the static report and interruptive alerts will guide health care providers towards medications best suited to the participant.

Inclusion/Exclusion Criteria	
Inclusion Criteria:
 
Acute Pain
 
 • Age \geq 8 years • English speaking or Spanish speaking • Elective/planned surgery types with planned or anticipated to be treated with tramadol, hydrocodone, or codeine pain management at an enrolling site, which may include orthopedic surgeries (e.g. arthroplasty, spine, etc.), open abdominal surgery, or cardiothoracic surgery and others 
Chronic Pain
 
 • Age \geq 18 years • English speaking or Spanish speaking • Seen at primary care clinics (such as, but not limited to, Internal Medicine, Family Medicine or Pediatrics) or patients seen in pain-relevant specialty clinics • History of pain for at least the last 3 months • Currently treated or being considered for treatment with tramadol, hydrocodone, or codeine to improve pain management 
Depression
 
 • Age \geq 8 years • English speaking or Spanish speaking • Patients followed at psychiatry clinics or primary care clinics at an enrolling site (such as, but not limited to, Internal Medicine, Family Medicine, or Pediatrics) • Documentation of depression and/or provider report of depression • Evidence of depressive symptoms for at least 3 months based on patient interview or documentation in electronic health records • Recent initiation of SSRI therapy, recent revised SSRI therapy, or anticipated need for revised or new SSRI therapy per health care provider
-------------------------------------	--

	
Exclusion Criteria
 
Trial-wide:
 
 • Life expectancy less than 12 months • Are too cognitively impaired to provide informed consent and/or complete study protocol • Are institutionalized or too ill to participate (i.e. mental or nursing home facility or incarcerated) • Have a history of allogeneic stem cell transplant or liver transplant • People with prior clinical pharmacogenetic test results for genes relevant for the study in which they will enroll (CYP2D6 for the pain studies and CYP2D6 or CYP2C19 for depression) or already enrolled in an ADOPT PGx trial • Any other medical, behavioral, or developmental condition that in the opinion of the investigator may confound study data/assessments 
Acute Pain
 
 • Receiving chronic opioid therapy, defined as use of opioids on most days for >3 months 
Chronic Pain
 
 • Plan to move out of the area within 6 months of enrollment • Undergoing treatment for an active cancer diagnosis • Currently taking daily opioids other than tramadol, codeine or hydrocodone for treatment of pain • Using a pain pump 
Depression
 
 • Plan to move out of the area within 6 months of enrollment • Have active psychosis or diagnosed psychotic disorders (schizophrenia, schizoaffective disorder, delusional disorder, psychotic depression, substance induced psychosis, schizopreniform disorder) • Have dementia or other neurocognitive disorders due to any cause, such as Alzheimer's disease, vascular/subcortical, lewy body disease, frontotemporal lobar degeneration • Have cognitive developmental delay and/or cognitive disability, including autism spectrum disorders (Note: ADHD is not an exclusion criteria) • Has a seizure disorder • Have bipolar disorder
Primary Endpoint	
Acute Pain: Silverman Integrated Analgesic Assessment (SIA) score (a composite of pain and opioid usage) at 10 days post-surgery in participants who are genetically or pheno-converted CYP2D6 IM or PM
 
Chronic Pain: Pain control, defined as change in the composite pain intensity score from baseline to 3-months in participants who are genetically or pheno-converted CYP2D6 IM or PM
 
Depression: Depression symptom control, defined as change in PROMIS depression 8A scores from baseline to 3-months in genetically or pheno-converted CYP2D6 UM/PM or CYP2C19 UM/RM/PM

Secondary Endpoints	
Acute Pain:
 
 • Pain intensity at 10 days post-surgery • Opioid usage at 10 days post-surgery • Prescription pain medication misuse score 3 months post-surgery • Mobility score 1-month post-surgery • Opioid persistence 6 months post-surgery 
Chronic Pain:
 
 • Pain reduction magnitude at 3-month follow-up, relative to baseline • Achievement of clinically significant pain reduction (30%) by 3-month follow-up, relative to baseline • Prescription pain medication misuse score at 3-month follow-up 
Depression:
 
 • Change in PHQ-8 scores between baseline and 3 months • Achieve 50% reduction in PHQ-8 scores at 3 months, relative to baseline • Medication side effects severity burden at 3 months • Participant medication adherence at 3 months • Achieve remission at 6 months defined as PROMIS depression score ≤ 16 • Achieve remission at 6 months, defined as PHQ-8 score ≤ 4 
All Trials:
 
 • Overall well-being at 6 months in all randomized participants • Concordance between metabolizer phenotype and prescribed medication • Sub-domains of the PROMIS 43 survey: pain interference, physical function, sleep disturbance, social role and activities functioning, fatigue, anxiety, and depression at 6-month follow-up
Statistical Analyses	
Acute Pain:
 
 • The effect of genotype guided opioid therapy on pain control will be determined by comparing the 10-day post-surgery SIA scores of the Intervention arm participant with CYP2D6 IM or PM phenotypes to the 10-day post-surgery SIA scores of the Control arm participant with CYP2D6 IM or PM phenotypes using a two-sided t-test or a two-sided Mann Whitney

- test, as appropriate, with a two-sided type 1 error rate of 0.049
- Similarly, the effect of genotype guided opioid therapy on all secondary endpoints will be compared between the Intervention arm CYP2D6 IM or PM phenotype and the Control arm CYP2D6 IM or PM phenotype using a two-sided t-test or a two-sided Mann Whitney test
- Additional analyses will include time trends in primary and secondary endpoints, subset analyses, covariate adjustments, and exploratory healthcare utilization and cost effectiveness analyses

Chronic Pain:

- The effect of genotype guided opioid therapy on pain control will be determined by comparing the change in baseline to 3-month follow-up composite pain scores of the Intervention arm participants with CYP2D6 IM or PM phenotypes to the change in baseline to 3-month follow-up composite pain scores of the Control arm participants with CYP2D6 IM or PM phenotypes using a two-sided t-test with type 1 error rate of 0.049
- Similarly, the effect of genotype guided opioid therapy on all chronic pain secondary endpoints will be compared between the Intervention arm CYP2D6 IM or PM subgroup and the Control arm CYP2D6 IM or PM subgroup using either a two-sided t-test or a test of two proportions, as appropriate.
- Additional analyses will include time trends in primary and secondary endpoints, subset analyses, covariate adjustments, and exploratory healthcare utilization and cost effectiveness analyses

Depression:

- The effect of genotype guided antidepressant therapy on depression symptoms will be determined by comparing the 3-month follow-up composite depression scores of the Intervention arm participant subgroup with CYP2D6 UM or PM or CYP2C19 UM, RM, or PM phenotypes to the 3-month follow-up composite depression scores of the Control arm participant subgroup with CYP2D6 UM or PM or CYP2C19 UM, RM, or PM phenotypes using a two-sided t-test with type 1 error rate of 0.049
- Similarly, the effect of genotype guided antidepressant therapy on all depression secondary endpoints will be compared between the Intervention arm CYP2D6 or CYP2C19 UM, RM or PM subgroup and the Control arm CYP2D6 or CYP2C19 UM, RM, or PM subgroup using either a two-sided t-test, a two-sided Mann Whitney test, or a test of two proportions, as appropriate.
- Additional analyses will include time trends in primary and secondary endpoints, subset analyses, covariate adjustments, and exploratory healthcare utilization and cost effectiveness analyses

All Trials:

- Overall well-being of all Intervention participants will be compared to the overall well-being of all Control participants at 6-month follow-up using ANOVA, adjusting for baseline differences in the two groups
- The effect of genotype guided therapy on concordance between phenotype and prescribed medication will be compared between Intervention and Control participants from the metabolizer phenotypic subgroups specified

	
for each trial's primary endpoint.
 
● Additional analyses will include time trends, subset analyses, and covariate adjustments analyses
--	---

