10. STATISTICAL ANALYSIS PLAN AND SAMPLE SIZE

10.1 Sample Size Determination

All trials power analyses are based on a modified intent to treat analysis, comparing the subset of intervention participants with have an actionable phenotype to the subset of control participants with an actionable phenotype. Effect sizes used to estimate power are based on prior studies of pain and depression pharmacogenetic testing and described below for each trial and shown in Table 8. Several steps were taken to generate a conservative sample size estimate. First, the power requirement was set to 90%. Second, sample sizes are adjusted for a 10% drop-out (for which UF has data from several studies that this is a good estimate). Third, slightly smaller effect sizes than what was observed in prior studies was used. Finally, sample size calculations are based on an alpha of 0.049, to allow one interim analysis with an alpha of 0.001 in each study.

Due to the study design and the delay in the control arm to obtaining the genotyping results required determine the actionable phenotype subgroup assignment, it is not feasible to directly monitor the number of randomized participants in the actionable subgroup for the enrollment stopping rule. Alternatively, the observed trial specific actionable phenotype percentages and the corresponding trial specific total enrollment targets will be used to identify when enrollment can conclude for a fully powered mITT study.

Acute Pain

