In the University of Florida's pilot acute pain study, the difference between study arms in SIA score was -38.55 with a SD of 93.5, for a standardized effect size of 0.412. Assuming a reduced standardized effect size of 0.375, 304 participants with an actionable phenotype per group, 152 from the intervention arm and 152 from control arm, are required to achieve 90% power for a two-sided two-sample t-test. Preliminary data from the University of Florida's acute pain study indicates the proportion of participants with an actionable phenotype, genotypic or pheno-converted CYP2D6 IM or PM, will be approximately 18%. After adjusting for the subset anticipated to have an actionable phenotype, 845 participants completing all assessments, per group, are required to achieve 90% power in the sub-group analysis (1678 total). Assuming 10% drop out or lost to follow-up and 7% of participants not going on to surgery, a total of 2020 randomized participants is required to sufficiently power this study. Factoring in variability in the proportion that are IMs or PMs (15% to 24%), 1516 to 2424 randomized subjects would be need to achieve 90% power in the mITT analysis.

Chronic Pain: In the University of Florida's prior chronic pain study, the difference between study arms in composite pain score was 0.6 with a SD of 1.4, for a standardized effect size of 0.43. The same effect size was observed when assessing 3-month changes in pain scores. Assuming a standardized effect size of 0.40, 268 participants within the specified subgroup, 134 from the intervention arm and 134 from control arm, are required to achieve 90% power for a two-sided two-sample t-test. Preliminary data indicate the proportion of participants with an actionable phenotype will be 30-35%; 10-15% of participants with an actionable genotype-based phenotype (CYP2D6 IM or PM) and an additional 20% with a pheno-converted PM/IM based on drug-drug-gene interactions. After adjusting for the subset anticipated to have an actionable phenotype, 447 participants completing all assessments, per group, are required to achieve 90% power in the sub-group analysis (894 total). Assuming 10% drop out or lost to follow-up, a total of 994 randomized participants is required to sufficiently power this study. Factoring in variability of the proportion of randomized population that are IMs or PMs (24-33%), 906 to 1244 randomized subjects would be need to achieve 90% power in the mITT analysis.

Depression:

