Study	Assumed Actionable Phenotype	Total N	Completed N (90% assumed)	Intervention	Usual Care	Intervention: Actionable Phenotype	Usual Care: Actionable Phenotype	Effect Size	Power
Acute Pain (CYP2D6 IM/PM)	18% (15%-24%)	2,020 (2424-1516)	1,690* (2028 - 1268)	845 (1014 - 634)	845 (1014 - 634)	152	152	0.375	90.00%
Chronic Pain (CYP2D6)	30% (24% - 33%)	994 (906 - 1244)	894 (814-1118)	447 (407-559)	447 (407-559)	134	134	0.4	90.00%
IM/PM)									
Depression (CYP2D6 or CYP2C19 PM/UM)	40% (up to 60%)	1,508 (1006)	1,356 (904)	678 (452)	678 (452)	271	271	0.28	90.00%
Total		4,522	3,940	1,970	1,970	557	557		

*Accounts for an additional 7% of participants not completing surgery

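### The acute-pain randomised target is about 1730 in the synopsis but 2020 in section 10.1 and Table 9, for the same 304 analysed participants, and no actionable rate is given for 1730

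*Combined protocol and SAP*

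**What the plan says.** The Study Population row of the synopsis gives the acute-pain randomised population as "Approximately 1730* participants with planned/elective surgery who are anticipated to start a paincontrol medication", and the analysed population as "Approximately 304 participants from the randomized population who have an actionable phenotype defined as CYP2D6 IM or PM". The asterisk leads to a footnote shared by all three trials: "Subject to change based on the actionable phenotype rates and missing data". The footnote states no rate and no level of missing data.

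Section 10.1 starts from the same 304 (152 per arm) and concludes that "a total of 2020 randomized participants is required to sufficiently power this study". Its inputs are a standardised effect of 0.375, 90% power, an 18% actionable rate, 10% drop-out and 7% not proceeding to surgery. On significance level it says that "sample size calculations are based on an alpha of 0.049". Table 9 repeats the total, with its range over actionable rates of 15% to 24%, as "2,020 (2424-1516" (in parentheses).

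Section 10.1 also explains how enrolment will end. Control-arm phenotypes arrive too late to count the analysis set directly, so "the observed trial specific actionable phenotype percentages and the corresponding trial specific total enrollment targets will be used to identify when enrollment can conclude". The stated aim is full power in the modified intent-to-treat set.

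**The concern.** Two parts of the current text give different randomised totals for one trial and attach the same analysed number to both. The gap is 2020 − 1730 = 290 participants, or 14% of 2020. The amendment log records enrolment numbers as updated in both the synopsis and section 10.1/Table 9 under the same date (8/30/23), so neither can be set aside as an untouched leftover.

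The total matters more here than in most trials. The analysis set cannot be counted during recruitment, and section 7.5 has control samples genotyped only after the 6-month assessment. The total, paired with an actionable rate, is therefore the working guide to when recruitment is complete. A total printed without its rate cannot be used in that way, and a reader cannot tell whether 90% power still applies to it.

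**Working it through.** **Inputs (section 10.1, Acute Pain).** Effect d = 0.375; two-sided α = 0.049; two-sample t-test; 1:1 allocation; actionable rate 18% (range 15–24%); drop-out 10%; no surgery 7%. Retained fraction: 0.90 × 0.93 = 0.837.

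**1. Reproduce the analysed number.** Power comes from the noncentral t distribution with df = 2n − 2 and noncentrality d√(n/2). At n = 152 per arm the noncentrality is 0.375 × √76 = 3.27 and power is 90.1%. At n = 151 it is 89.96%. So 152 per arm, 304 in total, is correct.

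**2. Reproduce the randomised number.** Rounding up at each step:
- 18%: 152/0.18 = 844.4 → 845 per arm, 1690 in total; 1690/0.90 → 1878; 1878/0.93 → 2020.
- 15%: 152/0.15 → 1014 per arm, 2028 in total; 2028/0.90 → 2254; 2254/0.93 → 2424.
- 24%: 152/0.24 → 634 per arm, 1268 in total; 1268/0.90 → 1409; 1409/0.93 → 1516.

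All three figures in Table 9 are recovered, so the plan's method is clear.

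**3. Carry 1730 through the same method.** Actionable completers = 1730 × 0.837 × rate.

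| Actionable rate | Completers | Power |
|---|---|---|
| 15% | 217 | 78.3% |
| 18% | 261 | 85.2% |
| 20% | 290 | 88.7% |
| 21% | 304 | 90.2% |
| 24% | 348 | 93.5% |

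At 18% the shortfall is 304 − 261 = 43 completers and about 5 points of power.

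**4. Rate implied by 1730.** 304/(1730 × 0.837) = 21.0%. This depends on attrition, which the footnote leaves open:
- losses added instead of multiplied (0.83 retained): 21.2%, with 85.0% power at an 18% rate;
- 10% drop-out only: 304/(1730 × 0.90) = 19.5%;
- no losses at all: 304/1730 = 17.6%.

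So 1730 could rest on any of several pairs of rate and attrition, and the text does not identify one.

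**5. The other two trials.**
- Chronic pain: 985 in the synopsis, 994 in section 10.1. 985 × 0.90 × 0.30 = 266 against 268 needed; power stays at 90%. Implied rate 268/(985 × 0.90) = 30.2%.
- Depression: 1540 against 1508. 1540 × 0.90 × 0.40 = 554 against 542 needed. Implied rate 542/(1540 × 0.90) = 39.1%.

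**6. Two slips in the acute-pain paragraph of 10.1.** For 845 per group it says they "are required to achieve 90% power in the sub-group analysis (1678 total"; but 2 × 845 = 1690, as in Table 9. It also calls 304 a per-group number, although the same sentence splits it into 152 and 152. Neither slip carries into 2020, which follows from 1690.

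**The case against.** The strongest reply is that the plan never pairs 1730 with 18%. Section 10.1 treats 2020 as one point on a range from 1516 to 2424, and 1730 lies inside it. The plan's own formula returns 1730 at 21%, a rate inside 15–24%, and there it delivers 304 and 90%. The footnote names actionable rates and missing data, the very inputs that would move the total. The enrolment rule uses observed rates with the corresponding total: if the observed rate is 18%, the corresponding total is 2020, and stopping at 1730 would depart from the rule. On this reading 1730 is simply a target updated to experience.

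Most of this stands. It rules out the stronger reading that a reader might infer, namely that the acute-pain trial is planned at 85% power or will stop short. The documents do not support that, because the loss requires both a rate near 18% and use of 1730 regardless.

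The reply does not remove the mismatch. That 1730 reflects an observed rate is inference, as no section states it. Section 10.1 and Table 9 still present 2020 as the requirement. Nor can the synopsis totals be read as values picked from within 10.1's ranges, since the depression figure of 1540 lies outside the stated 1006–1508.

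A further fair point is that 261 counts completers. Section 10.3 defines the analysis population without requiring completion, and section 10.8 imputes missing outcomes except after death. The comparison with 304 is still like with like, because section 10.1 also reaches 304 as completers and takes no credit for imputation.

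**Conclusion.** The inconsistency is certain: 1730 and 2020 both stand in current text for the same 304 participants, and the basis for 1730 is not given. Its consequence for power is conditional. At the plan's attrition and effect size, 1730 gives 90% power if the actionable rate is about 21%, 85% at the stated 18%, and 78% at the lower planning bound of 15%. These figures assume d = 0.375, two-sided α = 0.049, equal arms and power counted on completers, as in section 10.1. The chronic-pain and depression differences do not materially affect power, and the two slips are clerical. The point should be treated as a reconciliation of a stated sample size that helps decide when enrolment ends.

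**What to change.** - Give one acute-pain randomised target in the synopsis, section 10.1 and Table 9.
- If 1730 is in force, state the observed actionable rate and the attrition it rests on (about 21% at the planned attrition) and the power at that rate, with 85% shown as the figure at 18%. Otherwise align the synopsis to 2020.
- Align the chronic-pain (985 against 994) and depression (1540 against 1508) totals in the same edit.
- In the acute-pain paragraph of 10.1, change 1678 to 1690 and describe 304 as the total across both arms.

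The cost is protocol wording only. Endpoint, test, significance level and analysis population are untouched. The one possible price is a less favourable stated power, if 1730 is kept and the rate behind it proves to be below about 21% at the planned attrition.
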